## **7. ETHICAL CONSIDERATIONS**

### **7.1 Regulation statement**

The study will be conducted according to the principles of the Declaration of Helsinki and the privacy law (AVG).

### **7.2 Recruitment and consent**

Eligible patients will be invited by telephone or by e-mail by the practice nurse and will be asked for oral permission to approach him/her for participation in the study. If the patient is interested in participating, a patient infolder folder is shared and personal details (name, e-mail address and telephone number, and preference for information by e-mail or on paper) will be sent to the research team via a secure mail connection. After five days the patient is contacted by the research team to obtain informed consent. The research worker creates a study ID, records the data in the Access logistic database in the folder H:sleutelbestanden and in CASTOR. The study ID consists of the practice number plus a serial number and cannot be traced back to an individual. The researcher sends the CASTOR questionnaire for baseline measurement to the participant. A notification is set up in CASTOR so that a message is sent to the to the mailbox if a questionnaire has been completed. After receiving the notification, the research team informs the practice via secure mail that the participant can start with the new method of care.

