## 2. STUDY DESIGN

We will perform a cluster randomized controlled trial with a follow-up time of 12 months.

The three participating primary care cooperatives, i.e. Nijmegen, Arnhem, and Doetinchem, will recruit 15 general practices (clusters) who will be randomized using a 2:1 ratio in two study groups:

1. The intervention group: the GDM programme including a person-centered, integrated, and holistic approach
2. The control group: care as usual according the current SDM programmes

All practices will receive instructions from the research team on the procedures of the evaluation study. Participating practices will then start recruiting patients from a random sample of eligible patients, i.e. patients with DM2, COPD, or CVD who are currently receiving SDM. After written informed consent, information will be collected through questionnaires at baseline, 6 months and 12 months, and by interviews and data collection from electronic medical records. Information will also be collected from the participating healthcare providers through questionnaires and interviews.

In the two months prior to the start of the intervention, all practices in the intervention group will be trained in providing GDM by their own primary care cooperative. During follow-up two to three intervention meetings will take place including peer coaching and case study discussions.

Practices who are allocated to the usual care group will not receive any training, but will continue with their SDM programmes.

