### 3. TREATMENT OF SUBJECTS

#### 3.1 OPTIMA FORMA intervention

The core of GDM programme including person-centered and holistic approach is a cyclical process described in Figure 1. The practice nurse in the general practice will act as case manager. She/he can consult the general practitioner or other health providers when necessary. The first step in the intervention is assessing the integral health status of the patient (health across multiple domains, including physiological measurements and symptoms of disease), using a (preferably digital) questionnaire at home and physical measurements. The second step is an appointment in which the results are discussed with the patient in a semi-structured way. The case manager discusses if the results are recognizable, if there are other issues which haven't come up, and the priorities of the patient. Personal goals are formulated in the third step, which can range from purely medical goals to social goals. In the fourth step, the healthcare professional and patient will choose through shared-decision making the most appropriate interventions and support to achieve these goals. The goals and interventions are documented in a personal healthcare plan, which is preferably digitally available for all relevant healthcare professionals and the patient. Next, referrals are made if necessary and the treatment is started. An evaluation is planned and carried out, if necessary multiple times. If a treatment goal is reached or another treatment goal is more urgent, the cycle can be repeated.

[figure not shown]

Figure 1. Presentation of the cyclic process of the GDM programme

In order to provide the OPTIMA FORMA intervention to participating patients all healthcare professionals involved will be trained by their primary care cooperative on the concept of Positive Health, communication skills, use of materials and ICT, and interprofessional collaboration prior to the start of the intervention. During follow-up, the

practices will receive additional support from the primary care cooperative through intervision meetings and case report discussions.

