**Figure 2. Randomisation procedures in the OPTIMA FORMA and EMBOSS cluster RCTs**

After practices have been recruited, the practices will be randomised to the intervention or the usual care group. To avoid an imbalance between the randomised groups stratification will take place according to (i) the primary care cooperative, and (ii) the socioeconomic status of the practice population. Because of the nature of the intervention, it will not be possible to mask intervention allocation from the GPs or the patients. The research nurses who will collect the outcome data and the researchers who will perform the analyses will be blinded to treatment allocation.

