#### 7.4.2 Quantitative data

If the subject has indicated a preference for a paper version of the questionnaires, they will be sent by regular mail (including a reply envelope) and the data will be entered into Castor

EDC by the study employee. The papers are kept in a locked cabinet in room 3.20 (technical room number M245.03.350) for the duration of the project. Traceable data will be stored separately from the questionnaires for the duration of the pilot, i.e. in a different another locked cabinet, but in the same room. Afterwards, research data will be entered into the ELG archive (technical room number M245.-02.053). Identification Log and Informed Consent forms are stored in a closed cabinet in the ELG archive, thus separate from the data. In Castor no personal data is stored. The data is exported to SPSS for analysis. The pseudonymised data is stored for 15 years.

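### As the visible text most naturally reads, practices know their arm before their own nurse invites patients and before the self-reported baseline; first contact is unprotected and the primary model omits the baseline scores

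*Combined protocol and SAP*

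**What the plan says.** - **Randomisation.** Section 4.2, in the text under the Figure 2 caption: "After practices have been recruited, the practices will be randomised to the intervention or the usual care group". The same paragraph says that "it will not be possible to mask intervention allocation from the GPs or the patients", and that research nurses and analysts will be blinded.
- **Source of patients.** Section 2 describes the two arms, then instructions to all practices, and goes on: "Participating practices will then start recruiting patients from a random sample of eligible patients". It does not say who draws the sample, when, or whether a practice may depart from it.
- **First contact.** Section 7.2: "Eligible patients will be invited by telephone or by e-mail by the practice nurse". Section 3.1 describes the same person's part in the programme: "The practice nurse in the general practice will act as case manager".
- **From contact to baseline.** Section 7.2: "If the patient is interested in participating, a patient infolder folder is shared and personal details" go to the research team, which seeks consent after five days, makes the database entry and sends the baseline questionnaire. When that is returned, the team "informs the practice via secure mail that the participant can start with the new method of care". No randomisation step falls between baseline and the start of care.
- **Records.** Section 7.4.2: "Identification Log and Informed Consent forms are stored in a closed cabinet in the ELG archive". The content of that log is not given.
- **Analysis.** Section 6.1 adjusts for education, social support, smoking, age and sex. Baseline GMH, GPH and P3CEQ are not in the model.

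**The concern.** If a practice knows its arm when it invites, two things can differ between arms with no treatment effect.

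1. **Who enrols.** The nurse's approach, or the patient's willingness, may depend on the care on offer.
2. **How baseline is rated.** A patient who knows that a new programme is coming may rate current care differently from one who knows that nothing will change.

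Both bear on the primary outcome, because a responder is defined by change from this baseline on three self-reported scores. Blinding the research nurses and analysts does not help where the patient supplies the rating. Enrolment has an effect only through a score that is low or high by chance on the day, which then regresses. Enrolling patients whose stable scores truly differ leaves the change, and so the responder rate, unmoved.

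Patients who decline to the nurse never reach the research team in the process described. Without counts by arm, differential acceptance could not be examined afterwards.

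**Working it through.** **Inputs from Section 2.4.** Responder rates 20% and 35% (planned difference 15 points), ICC 0.03, 40 patients per practice, 20% loss to follow-up. **From Section 4.2:** 10 intervention and 5 control practices, plus 5 control practices from EMBOSS. **Assumed, because the plan gives no value:** the size, direction and persistence of any bias, and the correlations below.

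**The plan's own figure.** The plan has no figure on this point. Its sample size reproduces under 1:1 allocation: 138 per arm gives 276; the design effect on 32 completers is 1 + 31 × 0.03 = 1.93; 276 × 1.93 = 532.7; 532.7 / 0.8 = 665.8; 665.8 / 40 = 16.6, rounded up to 17 practices, or 680 patients. The fix does not change this number.

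**Simulation.** 1,000,000 patients per setting and no treatment effect. There are three normal scores with SD 1, each a stable part plus an occasion-specific error. Retest correlation is 0.6, 0.7 or 0.8, error correlation between scores 0, 0.3 or 0.5, and stable-score correlation 0.5. A responder has at least one score up by 0.5 SD or more and none down by 0.5 SD or more. If baseline P3CEQ is reported δ lower and a fraction q of that persists at follow-up, the measured change rises by δ(1 − q).

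The untuned responder rate is 28–38%. A common decline of 0.13–0.42 SD in both arms brings it to the plan's 20%. Results for a 0.2 SD shift in one arm, in percentage points:

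| Mechanism | Tuned to 20% | Untuned |
|---|---|---|
| Coloured baseline, none persists | 2.5–4.8 | 3.3–5.7 |
| Coloured baseline, half persists | 1.2–2.4 | 1.7–2.8 |
| Coloured baseline, all persists | 0 | 0 |
| Enrolment tilted on measured P3CEQ | 0.9–2.0 | 1.1–2.7 |

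A lower reported baseline raises the rate and a higher one lowers it by a similar amount. Tuning is itself a choice: reaching 20% through a retest correlation of 0.93 gives 3.8–9.1, 2.3–4.0 and 0 for the three coloured-baseline rows. The tuned column is therefore not an upper bound.

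**Adjusting for the three baseline scores** (logistic model with linear, quadratic and cross terms, untuned settings, 0.2 SD lower). The enrolment effect falls to between −0.4 and 0.0. Baseline-only colouring still leaves +1.9 to +5.2. If all of it persists, adjustment creates −0.6 to −1.3.

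**Effect on the test, 10 v 5 practices, 5-point shift.** Effective sizes are 5 × 32 / 1.93 = 82.9 and 10 × 32 / 1.93 = 165.8. The pooled rate is 0.233, the null SE 0.0569 and the alternative SE 0.0553. Rejection probability = Φ((0.05 − 1.96 × 0.0569) / 0.0553) + Φ((−0.05 − 1.96 × 0.0569) / 0.0553) = about 0.135, against a nominal 0.05. For a 3-point shift it is 0.079. With 10 v 10 practices the two figures are 0.193 and 0.102.

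**Could a baseline table settle it?** The design effect at enrolment is 1 + 39 × 0.03 = 2.17, taking the ICC to hold for baseline scores. With 10 v 10 practices the 95% half-width is 1.96 × √(2.17 × (1/400 + 1/400)) = 0.20 SD. With 10 v 5 it is 1.96 × √(2.17 × (1/400 + 1/200)) = 0.25 SD. A 0.2 SD shift could not be excluded.

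**The case against.** **The order is inferred.** In Section 2 the word introducing patient recruitment follows the instructions to practices, not a statement that allocation has been disclosed. Figure 2, which Section 4.2 says shows the combined randomisation, is not available. The closing sentence of Section 7.2 cannot apply to control practices and may come from the pilot, which Section 7.4.2 still mentions. This stands. A reader might infer that the plan states allocation before invitation; it does not. The visible text points that way and nothing in it points the other way.

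**Absence cannot be proved.** A reader might infer that no neutral wording or screening log exists. The documents do not support that: consent pages were removed, and the Identification Log is named without its content. What can be said is that none is described in the visible text. Even a neutral information folder would reach the patient only after the nurse's call or e-mail had produced interest.

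**The enrolment route is narrow.** Baseline is completed after consent, so the nurse has no study score to select on, and the sample is meant to be random. This also stands. The simulated tilt acts directly on the measured score and still yields only about 1 to 2 points.

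**The remedy does not reach the larger figures.** A frozen list and counts do nothing about coloured reporting, a neutral text helps only in part, and adjustment leaves most of it. This is correct, and the fix says so.

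**Conclusion.** The concern holds in a limited form. On the most natural reading, the nurse who will deliver the intervention makes first contact with allocation known, the baseline follows, and the primary model ignores the baseline scores. The existing safeguards are real but do not cover first contact.

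On assumed biases of 0.2 SD, tuned to a 20% rate, the possible distortion is about 1–2 points from enrolment and 0–4.8 points from coloured reporting, depending on persistence. Both are well below the planned 15 points. A reader might infer that the trial will be biased in favour of the intervention. The documents do not support that: they give no bias size, the direction is unknown, and patients stay unmasked, so some or all of any colouring could persist and cancel. The point merits correction because the enrolment part is cheap to prevent and hard to detect afterwards. It does not undermine the design. Confidence is medium, mainly because the order is inferred.

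**What to change.** **Sections 2, 4.2 and 7.2**

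1. State the order of practice randomisation, disclosure of the arm, patient invitation and baseline.
2. Draw each practice's random patient list in a fixed order and freeze it before that practice is randomised.
3. Invite in list order with one standard text that does not reveal the arm. The practice may still send it, so permission still comes before details are shared.
4. Record and report counts of invited, declined and consented patients by arm, with no personal data for those who decline. Seek the same counts for the EMBOSS control practices where available.

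**Section 6.1**

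5. Add an analysis adjusted for baseline GMH, GPH and P3CEQ. State that it addresses imbalance in measured baseline and not coloured reporting.

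**Optional.** Complete invitation and baseline before the arm is disclosed. Of these steps only this one would deal with coloured baseline reporting. It is optional because intervention practices are trained in the two months before the start, so it may delay training and the start of care.

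**Cost.** Steps 1–5 need one list, one text and one count log per practice, a little research-team time, and one extra model on data already collected. The EMBOSS counts depend on that trial's cooperation. If recruitment has begun, step 1, retrospective counts where they exist, and step 5 remain feasible.

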### **7.3 Benefits and risks assessment, group relatedness**

- The intervention has been developed by the three primary care cooperatives in close collaboration with their healthcare professionals and their patient panels and with the guidance of our research group. Also, input from the Dutch College of General Practitioners (NHG) and from InEen, the branch organisation for primary care

cooperatives, has been obtained to ensure that the intervention will suit their vision and future plans for reorganising Dutch primary care chronic disease management. The intervention is also in line with current movements in healthcare, such as the Positive Health concept.

- All three primary care cooperatives are intending to gradually implement the intervention throughout their regions in the upcoming years. Thus, the GDM programme will be implemented and will replace current SDM, even without the current cluster RCT as proposed in this study protocol.
- The burden and risks associated with the intervention are negligible and comparable with the usual care, i.e. the current SDM programmes.
- Patients in the control group will continue with their care as usual, i.e. single chronic disease management according to the protocols of the SMD programmes that have been used in the participating cooperatives since the last decade.
- The additional burden or risk associated with participation in this study is negligible. After written informed consent, patients in both groups will fill in a digital or paper questionnaire at baseline, 6 months, and 12 months. Estimated time to fill in the questionnaire is 20 minutes. A purposive sample of approximately 15 patients will participate in focus-groups interviews at the end of follow-up.

## ADMINISTRATIVE ASPECTS, MONITORING AND PUBLICATION

### 7.4 Handling and storage of data and documents

#### 7.4.1 Qualitative data

Personal data (i.e. name, home address, e-mail address, telephone number) are needed to identify subjects when contact is needed. The personal data is stored in an Access database (key table) and linked to a personal identification number (pseudonym). Only some researchers and the research assistant have access to this database. The database is stored in a separate, secure folder on the Radboudumc drive (H:sleutelbetanden/CL-Ketenzorg Ontketend). The pseudonym is used in ATLAS.ti to identify a test subject. We make audio recordings of the focus groups. These will be transcribed in Word and stored on These transcripts will not contain the names of the study subjects, only the pseudonyms (if necessary). The Word documents are permanently saved as PDF and imported into ATLAS.ti. The pseudonymised data are stored for 15 years.

#### 7.4.2 Quantitative data

If the subject has indicated a preference for a paper version of the questionnaires, they will be sent by regular mail (including a reply envelope) and the data will be entered into Castor

EDC by the study employee. The papers are kept in a locked cabinet in room 3.20 (technical room number M245.03.350) for the duration of the project. Traceable data will be stored separately from the questionnaires for the duration of the pilot, i.e. in a different another locked cabinet, but in the same room. Afterwards, research data will be entered into the ELG archive (technical room number M245.-02.053). Identification Log and Informed Consent forms are stored in a closed cabinet in the ELG archive, thus separate from the data. In Castor no personal data is stored. The data is exported to SPSS for analysis. The pseudonymised data is stored for 15 years.

### **7.5 Public disclosure and publication policy**

Science: The findings of the project will be published in international health-related scientific peer-reviewed journals, and will serve as the basis for the thesis of the GP trainee / PhD candidate on the project. Apart from the international papers, a summary paper with the main findings will be prepared for Dutch medical journal (Huisarts & Wetenschap, Nederlands Tijdschrift voor Geneeskunde). The results will also be presented at at least two international conferences on primary care or integrated care. On the national level, the results will be presented at the Dutch GP science day (NHG Wetenschapsdag) and the conferences of the GPs with special interest groups for respiratory care (CAHAG), diabetes care (DIHAG) and cardiovascular disease care (HartVaathAG), and at least one national conference on integrated care.

Clinical practice: During the final phase of the project, when the trial has been finished, the data have been analysed and the final results are available, a 1-day national symposium will be organized to present and discuss the findings and their implications. All relevant stakeholders will be invited for this symposium, i.e. representatives of all integrated general practice care groups ('zorggroepen') in the country, health policy makers (ministry of health (VWS), Zorginstituut Nederland, InEen, others), the professional organisations of GPs (LHV, NHG), practice nurses (V&VN Praktijkverpleegkundigen & Praktijkondersteuners), physiotherapists (KNGF), medical specialists (especially chest physicians/NVALT and internal medicine specialists/NIV), health insurance companies, relevant charities (Lung Foundation, Diabetes Foundation, Heart Foundation) and funding bodies (ZonMw, NutsOhra Fund), and patient organisations (NPCF) will be invited. The results will also be brought to the attention of the bodies responsible for the national clinical practice guidelines (NHG, Federation of Medical Specialists, others).

Education: If the GDM approach for patients with chronic diseases in primary care turns out to be effective, the training for practice nurses and GPs that is developed for the project will be made available to all (primary) care organisations that want to switch to this new approach. The best way to organize broad access to the training will be explored during the final year of the project. The preferred approach will probably be to use existing channels for postgraduate training of primary care professionals, for instance through the NHG (or its special interest groups) and V&VN. In the exploration we will also consider the best way to facilitate uptake of (parts of) the training in the vocational training programs for practice nurses

Society: Together with the PR/communication department of Radboudumc we will develop a strategy to disseminate the findings to the national press, to other popular media and directly to organisations that have an interest in the findings (e.g., health insurance companies, chronic care groups etc.). The investigators will be prepared to present and discuss the findings at non-scientific meetings (e.g., for health policy makers, regional care organisations etc., available time allowing) in the year after the project has finished.

The trial will be registered at [clinicaltrials.gov](https://clinicaltrials.gov)

All data will be made available from the principal investigator, upon reasonable request

